gonarthrosis (IA/PAAG-SI/OA/2019) was conducted, in which 72 patients aged over 50 years with a verified diagnosis of gonarthrosis in accordance with the criteria of the American College of Rheumatology (ACR) II-III radiological stage classification Kellgren-Lawrence received 1 to 2 injections (at 1-week intervals) of 4 mL of MD NOLTREXTM into the most affected (target) knee joint. The second injection was not performed if the severity of pain in the target knee joint decreased by 40— or more a week after the first injection. The study was performed to evaluate the effectiveness and safety of MD NOLTREXTM with this method of use in comparison with placebo.

The current study is planned to include patients who received at least one intra-articular injection of MY NOLTREX[™] in IA/PAAG-SI/OA/2019 study and underwent procedures during the 5-week Visit (25 weeks – 6 months after the injection). After completing all the procedures of Visit 5 and completing the corresponding electronic individual registration card (eCRF) forms in the IA/PAAG-SI/OA/2019 study, the investigator receives information about which group in the IA/PAAG-SI/OA/2019 study the patient was assigned to, i.e. whether he received injections of the study MD or placebo. After that, patients who received the studied MD will be asked to sign an informed consent form to participate in the open clinical trial IA/PAAG-SI/OA/2020.

Procedures of Visit 5 (25 weeks - 6 months after injection) of the placebo-controlled trial IA/PAAG-SI/OA/2019, if they coincide with the screening procedures of Visit 0 of the open trial IA/PAAG-SI/OA/2020 for patients who have agreed to participate in this study and are eligible to participate, will be considered as procedures Visit 0 of the open trial IA/PAAG-SI/OA/2020. Thus, Visit 5 of the IA/PAAG-SI/OA/2019 study coincides with the screening Visit (Visit 0) of the IA/PAAG-SI/OA/2020 study.

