Procedures at Visit 5 of study IA/PAAG-SI/OA/2019 (hereinafter referred to in the Protocol as Clinical study 1 - CS1) that coincide with the screening Visit procedures (Visit 0) in study IA/PAAG-SI/OA/2020 will be counted as the procedures of Visit 0 of study IA/PAAG-SI/OA/2020, there is no need to repeat the identical procedures of these visits.

- The signing of the informed consent;
- The collection of demographic data;
- Measurement of the body weight;
- Collection of complaints and anamnesis;
- Registration of concomitant therapy;
- Assessment of the main vital signs (blood pressure [BP], heart rate [HR], number of respiratory movements [RR], body temperature);
- Physical examination of joints;

- Completing an algofunctional questionnaire for evaluating the osteoarthritis index developed by researchers at the Western Ontario and McMaster Universities Osteoarthritis, WOMAC with an assessment of subscale pain (WOMAC-A), stiffness (WOMAC-B), and functional performance (WOMAC-C) (from *Visit 5 of CS1*);
- Assessment of the severity of pain in the target knee joint by 100-mm VAS (from *Visit 5 of CS1*);
- Evaluation of the effectiveness of treatment by the patient, parameter OEP (from *Visit 5 of CS1*);
- Evaluation of the effectiveness of treatment by the investigator, parameter OEI (from *Visit* 5 of CS1);
- Documenting the target knee joint (the same joint that was identified as the target in the IA/PAAG-SI/OA/2019 study);
- Clinical blood test (hemoglobin level, hematocrit, red blood cell count, white blood cell count, white blood cell formula, platelet count, ESR) (from *Visit 5 of CS1*);
- Biochemical analysis of blood (glucose, alanine aminotransferase [SPGT], aspartate aminotransferase [AST], alkaline phosphatase [ALP], gamma-glutamyltranspeptidase [GGTP], total bilirubin, creatinine, uric acid, rheumatoid factor) (from *Visit 5 of CS1*);
- Coagulogram (APTT, PT, prothrombin index, fibrinogen) (from *Visit 5 of CS1*);
- Blood tests for antibodies to human immunodeficiency virus (HIV), hepatitis b surface antigen (HBsAg) and antibodies to Hepatitis C Virus (anti-HCV]), syphilis (RW);
- General urinalysis (color, transparency, relative density, pH, glucose, protein, ketone bodies, urobilinogen) (from *Visit 5 of CS1*);
- Rapid urine test for pregnancy in women with preserved reproductive potential (from *Visit* 5 of CS1);
- Evaluation of inclusion/non-inclusion criteria;
- Issuing a patient's diary;
- Check AE and serious AE (SAE).

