- Physical examination of joints;
- Assessment of the severity of pain in the target knee joint using 100-mm VAS;
- Injection of the studied MD into the target joint cavity (only for patients of Group B, in which the severity of pain in the target knee joint using 100 mm VAS did not decrease by 40% or more compared to the assessment at Visit 3)
- Evaluation of the patient's diary;
- Return of the diary to the patient;
- Registration of AE and SAE;
- Evaluation of exclusion criteria.

Visit 5 (Week 25, Day 169 ± 2 , follow-up)

- Measurement of the body weight;
- Collection of complaints and anamnesis;
- Registration of concomitant therapy;
- Assessment of the main vital signs (BP, HR, RR, body temperature);
- Physical examination of joints;
- Radiography of the knee joints and documentation of parameters of joint space width (JSW) and joint space narrowing (JSN);
- Filling out algofunctional questionnaire WOMAC with an assessment of the subscales of pain (WOMAC-A), stiffness (WOMAC-B) and functional performance (WOMAC-C);

- Assessment of the severity of pain in the target knee joint using 100-mm VAS;
- Evaluation of the effectiveness of treatment by the patient, OEP parameter;
- Evaluation of the effectiveness of treatment by the investigator, OEI parameter;
- Clinical blood test (hemoglobin level, hematocrit, red blood cell count, white blood cell formula, platelet count, ESR);
- Biochemical blood test (glucose, ALT, AST, ALP, GGTP, total bilirubin, creatinine, uric acid, rheumatoid factor);
- Coagulogram (APTT, PT, prothrombin index, fibrinogen);
- General urinalysis (color, transparency, relative density, pH, glucose, protein, ketone bodies, urobilinogen);
- Evaluation of the patient's diary;
- Evaluation of the total number of paracetamol tablets taken (one tablet = 500 mg) using patient's diary, PARACETAMOL parameter;
- As per patient's diary, evaluation of the total number of NSAIDs allowed by the Protocol in case of paracetamol inefficiency (NSAIDs allowed by the Protocol in case of paracetamol inefficiency: diclofenac potassium tablets 50 mg, diclofenac sodium tablets 75 mg, naproxen tablets 500 mg, naproxen sodium tablets 550 mg, meloxicam tablets 7.5 mg, celecoxib tablets 200 mg), NSAID parameter;
- Registration of AE and SAE;
- Evaluation of exclusion criteria.

An unscheduled visit

The following procedures must be performed during the visit:

- Measurement of the body weight
- Collection of complaints and anamnesis;

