#### **3.1.3.** Analysis of efficacy parameters

Main efficacy parameters of the studied MD:

1. Change in the overall score on the WOMAC scale (WOMAC-T) on Visit 3 (week 13), Visit 5 (week 25) compared to the basal value on Visit 0 (screening) of the open study and compared to the basal value on Visit 1 (week 1) of the IA/PAAG-SI/OA/2019 study;

2. Change in the pain subscale score (WOMAC-A) on Visit 3 (week 13), Visit 5 (week 25) compared to the basal value on Visit 0 (screening) of the open study and compared to the basal value on Visit 1 (week 1) of the IA/PAAG-SI/OA/2019 study;

3. Change in the score for stiffness subscale (WOMAC-B) and functional performance (WOMAC-C) at Visit 3 (week 13), Visit 5 (week 25) compared to the basal value at Visit 0 (screening) of open study and compared to the basal value at Visit 1 (week 1) of the study IA/PAAG-SI/OA/2019;

4. The change in the severity of pain in the target knee on a 100-mm VAS at Visit 2 (week 1), Visit 3 (week 13), Visit 5 (week 25) compared to the basal value at Visit 0 (screening) of open safety study and compared to the basal value at Visit 1 (week 1) study IA/PAAG-SI/OA/2019;

5. Evaluation of the effectiveness of treatment by the patient, parameter OEP (on a scale from 1-clear deterioration to 6-significant improvement) on Visits 3 and 5 (parameters OEP-w13 and OEP-w25, respectively);

6. Evaluation of the effectiveness of treatment by the investigator, parameter OEI (on a scale from 1-clear deterioration to 6-significant improvement) on Visits 3 and 5 (parameters OEI-w13, OEI-w25, respectively);

7. Assessment of the total number of paracetamol tablets taken (one tablet = 500 mg) starting from day 1 on Visits 3 and 5 (PARACETAMOL -w13 and PARACETAMOL-w25, respectively);

8. Assessment of the total number of NSAID tablets taken starting from day 1 on Visits 3 and 5 (NSAID-w13 and NSAID-w25, respectively);

9. The parameter JSN of the target knee joint at Visit 5 of the open study compared to the basal value on Visit 0 of the IA/PAAG-SI/OA/2019 study retrospectively.

All performance parameters will be analyzed both among all patients included in open study no. IA/PAAG-SI/OA/2020 (using descriptive statistics) and in subgroups of patients:

- those who received only one course of injections in the placebo-controlled study IA/PAAG-SI/OA/2019;
- those who received two courses of therapy both in the placebo-controlled and at Visit 1 (and as per the indications at Visit 2) of the open study;

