- those who received two courses of therapy both in the placebo-controlled and at Visit 3
  (and as per the indications at Visit 4) of the open study.

For comparison between these subgroups, variance analysis will be used (for quantitative parameters other than those based on WOMAC), covariance analysis (for quantitative parameters based on WOMAC, in this case the initial value of WOMAC in the double-blind phase of the study will be used as a covariate, and the results will be presented as the average, calculated by the least squares method), or the "Chi-square" criterion (for qualitative parameters), followed by the application of multiple comparison criteria (if necessary).

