## 3.4. Applicable level of significance

Statistical analysis of all the presented efficacy and safety parameters will be carried out at a 5% significance level, using two-way versions of statistical criteria.

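### Joint space narrowing is tested between subgroups over about 48–50 weeks, but half to three quarters of that time comes before any second course

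*SAP*

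**What the plan says.** The IA/PAAG-SI/OA/2019 trial is called the 2019 study below.

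- **Outcome.** SAP 3.1.3 item 9 gives one contrast: "The parameter JSN of the target knee joint at Visit 5 of the open study compared to the basal value on Visit 0" of the 2019 study. SAP section 2 and the protocol's list of effectiveness parameters define it the same way. The WOMAC and VAS changes have two reference points: they are "compared to the basal value on Visit 0 (screening) of the open study and compared to the basal value on Visit 1 (week 1"), the latter in the 2019 study.
- **Films.** In the protocol's visit schedule, "Radiography of the knee joints and documentation of parameters of joint space width (JSW) and joint space narrowing (JSN") appears at open-study Visit 5 only. For open-study Visit 0, procedures of the 2019 study's Visit 5 "that coincide with the screening Visit procedures (Visit 0) in study IA/PAAG-SI/OA/2020 will be counted as the procedures of Visit 0". Many items in that list are marked as carried over, but radiography is not listed at all. Visit 3 has none either.
- **Subgroups.** There are three: no second course, a second course from Visit 1, and a second course from Visit 3. The protocol assigns patients by pain change since Visit 1 of the 2019 study and by ten bars to re-injection. SAP 3.6 acknowledges that the split follows need for treatment, but uses this only to justify not imputing missing data.
- **Test.** SAP 3.1.3 sends every effectiveness parameter to these subgroups: "For comparison between these subgroups, variance analysis will be used (for quantitative parameters other than those based on WOMAC"). A baseline covariate is provided for WOMAC only. SAP 3.4 adds: "Statistical analysis of all the presented efficacy and safety parameters will be carried out at a 5% significance level".

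**The concern.** That the subgroups are not randomised affects every effectiveness parameter. JSN has a further problem: the tested quantity includes change that took place before the patient was assigned to a subgroup, and no reading is planned that would separate the two periods.

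If a knee that narrows faster in the first half year also hurts more, its owner is more likely to be re-injected. The earlier narrowing is then counted in the two-course subgroup's total. A significant result could be read as a structural difference between one and two courses when it reflects progression before the second course. If narrowing and pain response are unrelated, the earlier period only adds noise.

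**Working it through.** The plan gives no power or effect-size figure for JSN to reproduce; 72 is a ceiling on enrolment. The check has three parts.

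**1. Timeline**

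Inputs from the protocol: the 2019 study's Visit 5 is 25 weeks, or 6 months, after injection; "Visit 5 of the IA/PAAG-SI/OA/2019 study coincides with the screening Visit (Visit 0) of the IA/PAAG-SI/OA/2020 study"; open-study Visit 1 is Day 1, Visit 3 is Day 84 and Visit 5 is Day 169. As a check on the day count, Day 0 to Day 169 + 2, counted inclusively, is 172 days, which matches the stated maximum participation.

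- Open-study part: 169 − 1 = 168 days (24 weeks).
- 2019 part: 24 or 25 weeks, i.e. 168 or 175 days.
- Total: 336 to 343 days, i.e. 48 to 49 weeks, or 50 weeks if the visit labels are added (25 + 25). The gap between Visit 0 and the first injection in the 2019 study is not stated and comes on top.
- Share before a second course at Visit 1: 168/336 = 50% to 175/343 = 51%.
- Share before a second course at Visit 3: (168 + 83)/336 = 75% to (175 + 83)/343 = 75%. That leaves 169 − 84 = 85 days, about 12 weeks.

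These are shares of time. They are shares of narrowing only if progression is constant.

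**2. False-positive rate with no effect of a second course**

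The documents give no SD for JSN, no subgroup sizes and no correlation r between first-half narrowing and the tendency to be re-injected. All are assumed.

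*Two groups of 36, no reading error, equal and independent halves.* Splitting at the median of the latent tendency gives a first-half difference of 2 × 0.798 × r SD. Dividing by √2 puts it on the scale of the total change. Non-centrality = that × √(36/2) = that × √18.

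- r = 0.2: 0.319/√2 = 0.226; × 4.243 = 0.96; two-sided 5% rejection about 16%.
- r = 0.3: 0.479/√2 = 0.339; × 4.243 = 1.44; rejection about 30%.

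*Simulation of the planned three-group analysis of variance.* N = 72; subgroup sizes 24/24/24 or 36/12/24; reading error 0.5 SD per film; correlation between halves 0 or 0.3; 4,000 runs per case; subgroups ranked by pain response alone.

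| r | Rejection rate |
|---|---|
| 0 | 4.5–5.3% |
| 0.2 | 12–15% |
| 0.3 | 21–29% |
| 0.5 | 53–72% |

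**3. Would a film at open-study Visit 0 cure it?**

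In the same simulation, with change measured from such a film, rejection is 4.4–5.3% if the halves are uncorrelated and 4.8–11.4% if they correlate at 0.3. The direct carry-in of earlier narrowing is removed; confounding by indication is not. The Visit 3 subgroup would still have about 12 weeks between that film and its second course.

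**The case against.** **Dilution.** A reader might infer that a true change in narrowing rate would show at only half or a quarter of its size. That does not follow. The analysis is of JSN change, not of a rate averaged over the interval. If a second course alters the rate by d per day from Day 1, it shifts the Visit 5 value by 168d from either baseline. Earlier progression adds variance. With equal, independent halves the standardised effect for the Visit 1 subgroup falls to 1/√2 = 0.71 of what a film at the start of the open study would give, or √(1.5/2.5) = 0.77 with reading error of 0.5 SD per film. If variance grows with time, the Visit 3 figure is √(85/343) = 0.50 of what a film at Visit 3 would give.

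**Missing film.** A reader might infer that no midpoint film exists. The documents do not show this, because the 2019 protocol is not among them. SAP 3.1.1 mentions an initial Visit 0 assessment of parameters similar to those of the 2019 study, but does not name JSN. What stands is that neither document plans to use a midpoint value.

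**Assumed link.** Nothing in the documents ties early narrowing to pain response, and at r = 0 there is no inflation. The bars to re-injection place some patients who are still in pain in Group B, which weakens the link and leaves even its direction uncertain. This objection stands, so the inflated rates are conditional.

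**Scope.** The study's main purpose is safety, its efficacy task names knee function and analgesic need rather than structure, and no section announces a structural conclusion on one against two courses. This limits the consequence. It does not make the planned test interpretable.

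**Conclusion.** The point holds. JSN is measured from before the first course to the end of the open study, no JSN value is planned at the start of the open study, and the total is tested at 5%, unadjusted, between subgroups formed midway. If JSN is recorded as a grade, the chi-square test would apply and the problem is the same, although the calculations above would not carry over.

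The time shares, about 51% before a second course at Visit 1 and about 75% before one at Visit 3, rest on the visit days and the 25-week length of the 2019 study. The false-positive rates of about 5% (r = 0), 12–16% (r = 0.2) and 21–30% (r = 0.3) combine the two calculations and depend on correlations that the documents do not supply. They show what could happen, not what will.

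This should be changed but is not critical: JSN is one of nine effectiveness parameters, and the main safety analysis is unaffected.

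**What to change.** In SAP 3.1.3:

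1. Take item 9 (JSN) out of the between-subgroup tests.
2. Keep the descriptive report already planned for all included patients, labelled as change since before the first course.
3. If JSN is also shown by subgroup, give no p-value and draw no conclusion on one against two courses. State the share of the interval that precedes the second course: about half for the Visit 1 subgroup and about three quarters for the Visit 3 subgroup.
4. Check whether a film from Visit 5 of the 2019 study exists. If so, also report the change from that film, descriptively, for the reason shown in part 3 of the working.

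This is a wording change to the SAP and needs no new visit or film. The cost is one subgroup p-value.
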